Postbaseline measurements are collected after study drug administration through Week 16 (Visit 8) or early discontinuation visit. Efficacy data collected at scheduled visits (e.g., eCOA, ClinRO) will be used in all analyses unless it is missing. If an assessment is missing at a scheduled visit, an unscheduled post-baseline assessment can be used provided it falls within the window interval as follows: a ± 2 day window is used for Visit 3 (Week 1), Visit 4 (Week 2), and Visit 5 (Week 4); and a ± 4 day window is used to Visit 6 (Week 8), Visit 7 (Week 12), and Visit 8 (Week 16). If there is more than 1 unscheduled visit within the defined visit window and no scheduled visit assessment is available, the unscheduled visit closest to the scheduled visit date will be used. If two unscheduled visits of equal distance are available, then the latter of the two will be used.

Postbaseline daily diary endpoints will be the mean of weekly visit windows (diary windows) anchored on day of first dose (Day 1) and day of Week 16 scheduled visit. Weeks 1-14 are defined as follows:

Week	Days
1	1-7
2	8-14
3	15-21
4	22-28
5	29-35
6	36-42
7	43-49
8	50-56
9	57-63
10	64-70
11	71-77
12	78-84
13	85-91
14	92-98

The Week 16 diary window is the 7 days prior to the scheduled Week 16 visit. If there is no Week 16 scheduled visit, the 7 days prior to the last visit (whether scheduled or unscheduled)

occurring after Day 105 constitutes the Week 16 diary window if one exists. If there is no visit on which to anchor the Week 16 diary window, the Week 16 interval and its associated mean are defined as missing. If there are less than 4 non-missing assessments in the Week 16 diary window, the interval can be extended up to 7 additional days, one at a time, to obtain the most recent 4 non-missing values. The assessment of whether 4 non-missing values exist in the Week 16 diary window, and subsequent extension of that window, does not consider censored data in window construction (i.e., they are counted as non-missing unless they are truly unobserved). If the Week 16 diary window has less than 4 non-missing values after extending the Week 16 diary window up to a maximum of 14 days, the Week 16 diary window is defined as 7 days and the mean of the window is missing.

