The lower bound of Week 15 diary window is defined as Day 99. The upper bound of the Week 15 diary window is the minimum of either Day 105 or the lower bound of the Week 16 diary window -1. Consequently, Week 15 may be less than 4 days if the Week 16 scheduled visit is before Day 112. Moreover, as Week 15 diary window cannot exceed 7 days, there could be daily assessments between Weeks 15 and 16 diary windows that do not fall into a diary window. If after constructing the diary windows, there are fewer than 4 non-missing values the mean for that particular window is missing and subject to imputation rules.

The postbaseline value of the actigraphy analyses will be analyzed similarly through Week 4 (Visit 5) or early discontinuation but will include time. Thus, Week 1 will be the mean of the 7 days of actigraphy events which has a start date and time occurring within 168 hours of the date and time of first study drug administration. The Week 2, Week 3 and Week 4 scores will be similarly defined. If there are less than 4 non-missing assessments occurring in at least 4 separate 24-hour increments, the weekly interval will be missing. Furthermore, as some analyses require use of the primary censoring rule, assessments collected on the day of rescue or afterwards will be excluded from the weekly visit interval calculation when implementing the rule for daily diary and actigraphy analyses. If, after exclusion of these records, there are less than 4 non-missing assessments, the weekly interval which implements the primary censoring rule will be missing. The post-study follow-up weekly score for daily diaries will be calculated as the mean of the 7 days prior to the follow-up visit which occur after last dose of study treatment.

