6.4. Handling of Dropouts or Missing Data

Intercurrent events (ICH E9 R1) are events which occur after the treatment initiation and make it impossible to measure a variable or influence how it would be interpreted.

Depending on the estimand being addressed, different methods will be used to handle missing data as a result of intercurrent events. Intercurrent events can occur through the following:

- application of one of the censoring rules (including after permanent study drug discontinuation or after rescue therapy)
- discontinuation
- missing an intermediate visit prior to discontinuation or rescue
- lost to follow-up.

Non-censor intercurrent events are events that are not due to the application of any censoring rule, i.e., the last 3 items in the list above.

Note that as efficacy and health outcome data can accrue after a patient permanently discontinues study drug or begins rescue therapy, specific general censoring rules to the data will be applied to all efficacy and health outcome observations subsequent to these events depending on the estimand being addressed. These specific censoring rules are described below.

The *primary censoring rule* will censor efficacy and health outcome data after permanent study drug discontinuation or after rescue therapy. This censoring rule will be applied to all continuous and categorical efficacy and health outcome endpoints. This censoring rule is equivalent to using all the data up to rescue.

A *secondary censoring rule* will only censor efficacy and health outcome data after permanent study drug discontinuation. This sensitivity analysis will include all observed values up to study drug discontinuation. The secondary censoring rule will be applied to primary and key secondary efficacy and health outcome endpoints as sensitivity analyses.

[Table JAHM.6.1](#) describes the planned imputation methods for efficacy and health outcome endpoints with associated censoring rules. Sections [6.4.1](#) through [6.4.5](#) summarize the methodology of each imputation rule.

Table JAHM.6.1. Imputation Techniques for Various Variables

Efficacy and Health Outcome Endpoints	Imputation Method
IGA(0,1), EASI75, 4-point Itch NRS improvement, EASI90, SCORAD75	NRI ^{ab} , pMI ^a , Tipping point ^a
EASI percent change, ADSS Item 2 change, Skin Pain NRS change	MMRM ^{ab} , mLOCF ^a , pMI ^a
All remaining categorical measures	NRI ^a
All remaining continuous efficacy and health outcome measures	MMRM ^a , mLOCF ^a

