6.4.1. Nonresponder Imputation

A NRI method imputes missing values as non-responses and can be justified based on the composite strategy for handling intercurrent events (ICH E9 R1). This imputation procedure assumes the effects of treatments disappear after the occurrence of an intercurrent event defined by the associated censoring rule.

All categorical endpoints will utilize the NRI method after applying the primary censoring rule to patients who permanently discontinued study drug or were rescued (described in Section 6.4). Additionally, all primary and key secondary categorical endpoints will utilize NRI after applying the secondary censoring rule as sensitivity analyses. For analyses which utilize either of the censoring methods, randomized patients without at least 1 post-baseline observation will be defined as nonresponders for all visits.

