6.11.2. Secondary and Exploratory Efficacy Analyses

For secondary analysis, the null hypotheses is that neither baricitinib 4-mg nor baricitinib 2-mg is superior to placebo in the ITT population. These analyses assume treatment response disappears after patients are rescued or permanently discontinued from treatment and will serve as the primary estimand. In this estimand, missing data due to the application of the primary censoring rule and the occurrence of other non-censor intercurrent events will be imputed using the method described in Table JAHM.6.1.

A supplemental estimand for secondary endpoints is to test the null hypotheses that neither baricitinib 4-mg nor baricitinib 2-mg is superior to placebo in the ITT population. These analyses assumes the treatment response disappears after patients permanently discontinued from treatment. In this supplemental estimand, missing data due to the application of the secondary censoring rule and the occurrence of other non-censor intercurrent events will be imputed using the method described in Table JAHM.6.1.

A list of exploratory endpoints are provided in Section 4.2.2. There will be no adjustment for multiple comparisons for exploratory endpoints. The secondary and exploratory efficacy endpoints are detailed in Table JAHM.6.4 and analyses are provided in Table JAHM.6.5. Health outcomes analyses are described in Section 6.12.

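### A patient rescued late in a 7-day diary window can still count as a 4-point itch responder for that week, although the SAP says response disappears at rescue

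*SAP*

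**What the plan says.** **Scoring the week.** Section 6.2.2 averages daily diary entries over 7-day windows: Days 1-7 for Week 1, Days 8-14 for Week 2 and Days 22-28 for Week 4. For the last time point, "The Week 16 diary window is the 7 days prior to the scheduled Week 16 visit". When the primary censoring rule is in force, "assessments collected on the day of rescue or afterwards will be excluded from the weekly visit interval calculation". Then: "If, after exclusion of these records, there are less than 4 non-missing assessments, the weekly interval which implements the primary censoring rule" is set to missing. When the Week 16 window is built, censored days still count as available, so censoring alone does not move the window back.

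**Censoring.** Under Section 6.4 the primary rule "will censor efficacy and health outcome data after permanent study drug discontinuation or after rescue therapy". The secondary rule censors only after permanent discontinuation of study drug.

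**Imputation and estimand.** Section 6.4.1 applies nonresponder imputation (NRI) to all categorical endpoints, justifies it by the composite strategy, and imputes only values that are missing. It adds: "This imputation procedure assumes the effects of treatments disappear after the occurrence of an intercurrent event defined by the associated censoring rule". Section 6.11.2 says of the secondary analyses: "These analyses assume treatment response disappears after patients are rescued or permanently discontinued from treatment".

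**Endpoint.** Table JAHM.6.6 defines itch response as a change in the weekly score of -4 or lower in patients with baseline Itch NRS of at least 4. It is a key secondary endpoint at Weeks 1, 2, 4 and 16.

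**The concern.** Under a composite strategy the event itself decides the outcome: a patient rescued by the time of assessment is a nonresponder. Here the deciding factor is how many diary entries precede the event. If 4 or more remain, the weekly score is observed, NRI has nothing to impute, and the patient is classified on pre-rescue itch.

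The same event can then give opposite results at Week 16. A patient rescued a few days before the visit is a nonresponder on IGA and EASI75, because the visit data are censored, but may be a responder on itch. These endpoints belong to one multiplicity-controlled family (Section 6.6), in which itch response accounts for 4 time points × 3 doses = 12 hypotheses.

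The planned Week 16 sensitivity analyses would not reveal this. Placebo multiple imputation and the tipping-point analysis (Sections 6.4.4 and 6.4.5) both apply the primary censoring rule and impute only missing outcomes, and this weekly score is not missing.

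**Working it through.** The SAP gives no figure for rescue or drug discontinuation inside diary windows, so there is none to reproduce. The power statement in Section 6.1 concerns the primary endpoint and is unaffected.

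**1. Entries left after rescue.** Inputs from Section 6.2.2: window of 7 days, rescue day excluded, minimum of 4 entries. With a complete diary, rescue on window day *d* leaves *d* − 1 entries.

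| Rescue on window day | 1 | 2 | 3 | 4 | 5 | 6 | 7 |
|---|---|---|---|---|---|---|---|
| Entries left | 0 | 1 | 2 | 3 | 4 | 5 | 6 |
| Weekly score | missing | missing | missing | missing | observed | observed | observed |

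Days 1-4 lead to NRI and days 5-7 do not. If rescue days are evenly spread, the share that escapes is 3/7 = 43%.

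**2. Can such a patient be a responder?** Take baseline 8, a score of 4 on each of window days 1-4, and rescue on day 5. The weekly mean is (4+4+4+4)/4 = 4 and the change is 4 − 8 = −4.0, which meets the definition.

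**3. Contrast at Week 16.** With the visit on Day 113, the window is Days 106-112. Rescue on Day 110 leaves Days 106-109, which is 4 entries and an observed score. IGA and EASI75 on Day 113 come after rescue, are censored, and become nonresponse.

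**4. Incomplete diaries.** Let each day be completed independently with probability *c* (an assumption). The share that escapes is [P(4 of 4) + P(≥4 of 5) + P(≥4 of 6)]/7:
- *c* = 0.9: (0.656 + 0.919 + 0.984)/7 = 37%
- *c* = 0.8: (0.410 + 0.737 + 0.901)/7 = 29%
- *c* = 0.7: (0.240 + 0.528 + 0.744)/7 = 22%

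This ignores the backward extension available for Week 16 when fewer than 4 entries exist.

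**5. Permanent discontinuation.** The day-level exclusion in Section 6.2.2 names rescue only, and Section 6.4 censors data after discontinuation. If the stop day is excluded, the counts are as in step 1. If it is kept, a stop on day *d* leaves *d* entries, so stops on days 4-7 leave 4-7 entries and keep a score. A score can survive either way, but the count is not fixed.

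**6. Size.** The SAP gives no event rates. Assume that 1-10% of patients are rescued within the window week and that 5-25% of those already have a pre-rescue mean improved by 4 points. With full diaries, the share of an arm affected is rescue rate × 3/7 × share improved:
- low: 0.01 × 3/7 × 0.05 = 0.02 percentage points
- high: 0.10 × 3/7 × 0.25 = 1.07 percentage points

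Applied to the planned arms, the high case is 2.6 of 240 placebo patients or 1.3 of 120 on a baricitinib dose. One affected patient moves a full arm's rate by 1/120 = 0.8 points or 1/240 = 0.4 points. These are minimum shifts, because the endpoint counts only patients with baseline itch of at least 4.

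**The case against.** The best defence is that this is a stated choice. Section 6.2.2 addresses rescue inside a window directly, and Section 6.4 describes the primary rule as equivalent to using all data up to rescue. The estimand text speaks of effects disappearing after the event, and a mean built only from earlier days credits nothing after it. Section 6.11.2 is also generic: it covers continuous endpoints too, for which Section 6.4.2 says MMRM implies a different, hypothetical estimand.

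Part of this stands. Using pre-rescue data suits the continuous diary endpoints, and the 4-entry rule should stay there. It does not suit the binary endpoint, which Section 6.4.1 places under the composite strategy with all other categorical endpoints. Nor does it explain why one event before the Week 16 visit is nonresponse on IGA and EASI75 but can be response on itch.

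The objection on size also stands. A retained patient changes the result only if already improved by 4 points, and Section 6.4.3 itself expects data just before rescue or dropout to show a poor response.

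A final objection concerns the remedy. Making every event up to the last window day a nonresponse could create the reverse mismatch. If the Week 4 visit is on Day 27 and rescue starts after its assessments, IGA and EASI are kept, yet itch over Days 22-28 would be forced to nonresponse. The cut-off therefore has to refer to the visit assessments.

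**Conclusion.** The inconsistency is real for rescue. On days 5-7 of a complete window the weekly itch score survives, NRI is not triggered, and nothing else in the SAP makes the patient a nonresponder for that week. The likely effect is small: 0.02 to 1.07 percentage points of an arm on the assumptions in step 6, with unknown direction.

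A reader might infer more than the SAP supports:
- **That 43% of rescued patients are misclassified.** The figure is a share of rescues falling inside an analysis window, and it needs full diaries and evenly spread rescue days. Only those already improved by 4 points change the response rate.
- **That 3/7 and 4-6 retained entries also hold for stopping study drug.** The day rule names rescue only, so for discontinuation neither figure is fixed.
- **That the results are biased towards baricitinib, for instance through adverse-event stops in responders.** The SAP gives no rescue or discontinuation rates by arm, so no direction can be stated.
- **That itch and the visit-based endpoints always disagree.** The contrast is certain for Week 16, where the window ends before the visit. At Weeks 1, 2 and 4 it depends on when the visit falls.

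**What to change.** For the binary 4-point itch endpoint only (Weeks 1, 2, 4 and 16), add a derivation rule to Section 6.2.2 or 6.4.1:
- Set the patient to nonresponder for a diary window and all later windows if rescue or permanent discontinuation of study drug occurs within or before that window and before that week's scheduled visit assessments, however many pre-event entries remain.
- If there is no such visit, use the last day of the window as the cut-off.
- Under the secondary censoring rule, apply this to discontinuation only.

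State separately whether the day of permanent discontinuation is excluded from the weekly score. Keep the 4-entry rule for the continuous endpoints analysed by MMRM.

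The cost is a short SAP addition and one flag in the itch-response derivation. Itch response rates may be slightly lower in some arms.

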6.2.3. Analysis Methods

The main analysis method of categorical efficacy variables and health outcomes variables will use a logistic regression analysis with region, baseline disease severity (IGA), baseline value and treatment group in the model. Firth's correction will be used in order to accommodate (potential) sparse response rates. The p-value for the odds ratio from the logistic regression model will be used for statistical inference, unless Firth's correction still results in quasi-separation. In that case, Fisher's exact test will be used for statistical inference. The difference in percentages and 100(1-alpha)% confidence interval (CI) of the difference in percentages using the Newcombe-Wilson method without continuity correction will be reported. The p-value from the Fisher's exact test will also be produced as a secondary analysis.

The main analysis method for all continuous efficacy and health outcomes variables will use mixed model repeated measures (MMRM) analysis. The MMRM model will use a restricted maximum likelihood (REML) estimation. The model will include treatment, region, baseline disease severity (IGA), visit, and treatment-by-visit-interaction as fixed categorical effects and baseline and baseline-by-visit-interaction as fixed continuous effects. For daily diary assessments, the model for analyses up to Week 16 will include all weekly assessments. An unstructured (co)variance structure will be used to model the between- and within-patient errors. If this analysis fails to converge, the heterogeneous autoregressive [ARH(1)], followed by the heterogeneous compound symmetry (CSH), followed by the heterogeneous Toeplitz (TOEPH) will be used. The Kenward-Roger method will be used to estimate the degrees of freedom. Treatment least squares means (LSM) will be estimated within the framework of the MMRM using type 3 sums of squares. Differences in LSM between each dose of BARI and placebo (and associated p-values, standard errors and 95% CI) will be used for statistical inference. The LSM difference, standard error, p-value and 95% CI will be reported.

Treatment comparisons for continuous efficacy and health outcomes variables may also be made using analysis of covariance (ANCOVA) for primary and key secondary objectives. When an ANCOVA model is used, the model includes region, baseline disease severity, treatment group, and baseline value. Treatment LSM will be estimated within the framework of the ANCOVA using type 3 sums of squares. Reported differences in LSM and associated p-values, standard errors and 95% CI will be used for statistical inference. Treatment-by-region interaction will also be added to the model for sensitivity purposes and is discussed in Section 6.5.

Beginning on Day 14 a Cox proportional hazard (CPH) model of time (in days) to first observance of a 4-point itch reduction with effects for treatment, region, baseline mean itch, and disease severity will be used to test for treatment differences from placebo. For this analysis, daily itch scores will be compared to the baseline to determine if a 4-point itch reduction has been achieved in patients with a baseline itch of at least 4. The baseline for itch NRS is defined in Section 6.2.2. The day on which the first 4-point reduction in itch NRS is achieved will be modeled. If any significant treatment difference is observed then the same analysis will be performed on Day 13. This process of evaluating at the next lowest day will proceed until no significant differences are observed. No adjustments for multiple tests and multiple comparisons will be used. This analysis uses the Primary Censoring Rule for patients who are rescued or permanently discontinue study drug (see Section 6.4). Missing daily itch data will be replaced using NRI rule which means missing data is replaced with a non-response which would entail replacing missing values with a time to event of > 14 days, censored; >13 days, censored, etc., depending on the window being used. If the model assumptions for the CPH model do not hold, a log-rank test will be used.

Restricted mean survival time will be evaluated at Days 2, 3, 4 and 5 as an exploratory analysis. The model will include terms for baseline disease severity (IGA), baseline itch, region and treatment group.

Fisher's exact test will be used to test for differences between each baricitinib dose and placebo in proportions of patients experiencing adverse events (AEs), discontinuation from study drug,

and for other categorical safety data. Continuous vital signs, body weight, and other continuous safety variables, including laboratory variables will be analyzed by an ANCOVA with treatment group and baseline value in the model. The significance of within-treatment group changes from baseline will be evaluated by testing whether or not the treatment group LSM changes from baseline are different from zero; the standard error for the LSM change will also be displayed. Differences in LSM will be displayed, with the p-value associated with the LSM comparison to placebo and a 95% CI on the LSM difference also provided. In addition to the LSMs for each group, the within-group p-value for the change from baseline will be displayed.

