4.3. Exploratory Objectives

The exploratory objectives of this study are the following:

Objectives/Endpoints

• Mean change from baseline in nocturnal itch assessed by actigraphy device at 1 week and 4 weeks• Frequency of patient-reported “no itch” (Itch NRS score = 0) days from daily diaries from Week 12 to Week 16• Frequency of patient-reported “no pain” (Skin Pain NRS score = 0) days from daily diaries from Week 12 to Week 16• Mean change from baseline in the score of Item 1 of the ADSS at 1 week and 16 weeks• Mean change from baseline in the score of Item 3 of the ADSS at 1 week and 16 weeks• To evaluate changes from baseline in immunoglobulin E levels during the study• To evaluate changes from baseline in eosinophil levels during the study• To characterize baricitinib pharmacokinetics in the AD population and explore relationships between baricitinib exposure and study endpoints• To assess time to 4-pt itch reduction during the first 14 days after initiation of treatment• To assess time to improvement in Skin Pain during the first 14 days after the initiation of treatment• To assess the use of rescue therapy through the weight of sponsor provided topical corticosteroid and number of days not using rescue therapy

5. Study Design

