5.1. Summary of Study Design

Study I4V-MC-JAHM (JAHM) is a Phase 3, multicenter, randomized, double-blind, placebo-controlled, parallel-group, outpatient study evaluating the efficacy and safety of baricitinib 1-mg once daily (QD), 2-mg QD, and 4-mg QD as compared to placebo in adult patients with moderate to severe AD. The study is divided into 3 periods, a 5-week Screening period, a 16-week Double-Blinded Treatment period, and a 4-week Post-Treatment Follow-Up period. For those patients who complete the 16-week treatment period, there is an option to participate in the long-term extension study I4V-MC-JAHN (JAHN).

Approximately 600 patients ≥ 18 years of age who have responded inadequately to or who are intolerant to topical therapy will be randomized at a 2:1:1:1 ratio to receive placebo QD, baricitinib 1-mg QD, baricitinib 2-mg QD, or baricitinib 4-mg QD (240 patients in the placebo group; 120 patients in each baricitinib treatment group). Patients will be stratified at randomization according to disease severity (IGA 3 vs. 4) and geographic region.

Study JAHM will consist of 3 periods:

- Period 1: Screening period is between 8 and 35 days prior to Week 0 (Visit 2)
- Period 2: Double-Blind, Placebo-Controlled Treatment period from Week 0 (Visit 2) through Week 16 (Visit 8)
- Period 3: Post-Treatment Follow-Up period from last treatment visit at Week 16 (Visit 8) or Early Termination Visit (ETV) to approximately 28 days after the last dose of investigational product

[Figure JAHM.5.1](#) illustrates the study design. The blinding procedure is described in the Protocol.

[figure not shown]

Figure JAHM.5.1. Illustration of study design for Clinical Protocol I4V-MC-JAHM.

Abbreviations: AD = atopic dermatitis; eGFR = estimated glomerular filtration rate; PPD = purified protein derivative; QD = once daily; V = visit; W = week.

- Applicable to patients taking topical treatments (excluding emollients) or systemic treatments for AD at the time of screening.
- For patients randomized to the 4-mg once daily dose who have renal impairment (defined as eGFR <60 mL/min/1.73 m²), the baricitinib dose will be 2-mg once daily.
- Patients for whom PPD skin test for the evaluation of tuberculosis infection was performed at V1 must return and PPD test must be read 48 to 72 hours after Visit 1 (post-PPD).
- Occurs approximately 28 days after the last dose of investigational product. Not required for those patients entering the long-term extension study JAHN.

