6.2. General Considerations

This plan describes *a priori* statistical analyses for efficacy, health outcomes, and safety that will be performed.

Statistical analysis of this study will be the responsibility of Eli Lilly and Company (Lilly). The statistical analyses will be performed using SAS® Version 9.4 or higher.

Not all displays described in this SAP will necessarily be included in the clinical study report (CSR). Not all displays will necessarily be created as a “static” display. Some may be incorporated into interactive display tools instead of or in addition to a static display. Any display described in this SAP and not included in the CSR will be available upon request.

Statistical tests of treatment effects and CIs will be performed at a 2-sided significance level of 0.05, unless otherwise stated (e.g., graphical multiple testing strategy in Section 6.6).

Data collected at early termination visits will be mapped to the closest scheduled visit number for that patient if it falls within the visit window as discussed in Section 6.2.2. For by-visit summaries, only visits in which a measure was scheduled to be collected will be summarized. Any unscheduled visit data will be included at the patient-level listings. However, the data will still be used in other analyses, including shift analyses for safety analytes, change from baseline using modified last observation carried forward (mLOCF) for efficacy analyses, and other categorical analyses including safety.

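### The exploratory itch-onset Cox sequence continues for every dose while any one dose is significant, so a dose that failed at Day 14 can be tested on up to 13 earlier days

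*SAP*

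**What the plan says.** Section 6.2.3 sets the starting point: "Beginning on Day 14 a Cox proportional hazard (CPH) model of time (in days) to first observance of a 4-point itch reduction", with terms for treatment, region, baseline mean itch and disease severity, which "will be used to test for treatment differences from placebo". There are three doses, and Section 5.1 gives the arm sizes: "240 patients in the placebo group; 120 patients in each baricitinib treatment group".

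The continuation rule is "If any significant treatment difference is observed then the same analysis will be performed on Day 13". The stopping rule is "This process of evaluating at the next lowest day will proceed until no significant differences are observed". The same paragraph adds "No adjustments for multiple tests and multiple comparisons will be used".

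The level comes from Section 6.2: "Statistical tests of treatment effects and CIs will be performed at a 2-sided significance level of 0.05, unless otherwise stated". The endpoint is listed among the exploratory objectives in Section 4.3: "To assess time to 4-pt itch reduction during the first 14 days after initiation of treatment". Sections 6.6 and 6.11.2 confirm that nothing outside the graphical procedure, and no exploratory endpoint, is adjusted.

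**The concern.** A backward sequence that stops at the first failure has a useful property when it is run for one comparison at a time. A dose can have a significant day only if its Day 14 test is significant, so its chance of any false-positive day equals the error of that one test. No alpha has to be spent to get this.

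The rule as written loses that property because the gate is shared. Continuation needs only one significant dose, the analysis repeated is the one with all doses, and stopping requires that no dose is significant. A dose that failed at Day 14 is retested at Days 13, 12 and so on for as long as another dose stays significant. The plan also does not say how to read a dose with broken results, for example not significant at Day 14 but significant at Day 6.

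At stake is the interpretation of onset for the less effective doses. A stray early p-value could be taken as evidence of rapid action for a dose that showed no difference over the full 14 days.

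**Working it through.** **The plan's own figures.** The SAP states no error rate or power for this procedure. Its only design figure is power above 90% for the primary endpoint (Section 6.1). It reproduces for 240 vs 120 patients at 2-sided 0.05: 94.8% for 2 mg (25% vs 10%) and 99.5% for 4 mg (30% vs 10%). It has no bearing on the itch sequence.

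**Number of tests.** Day 14 down to Day 1 is 14 tests per dose. Every dose has the Day 14 test under any rule, so the shared gate adds at most 14 − 1 = 13.

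**Crude bound.** For 14 independent tests, 1 − 0.95^14 = 51%. This is far too high here, because each day's data set is nested in the next and the tests are strongly correlated. Simulation is needed.

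**Inputs from the SAP.** 240 placebo and 120 per dose; 2-sided 0.05 per test; start at Day 14; continue while any dose is significant.

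**Assumed inputs (not in the SAP).** Placebo event rate by Day 14 of 5%, 10%, 20% or 30%, with constant daily hazard h = 1 − (1 − rate)^(1/14). One dose with no effect. One effective dose at +20 or +30 percentage points. Share of patients with baseline itch of at least 4: 85% or 100%.

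**Method.** 40,000 simulated trials per setting. For each day the log-rank statistic (the Cox score test without covariates) is Z = U/√V on data up to that day, where U sums observed minus expected events in the dose arm and V is its hypergeometric variance. A day is significant if |Z| > 1.96. The placebo arm is shared.

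**Results for the dose with no effect, 100% eligible:**

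| Placebo Day-14 rate | Day 14 only (= gated by dose) | Shared gate, other dose +20 | Shared gate, other dose +30 | All 14 days run | All 14 days, favourable direction |
|---|---|---|---|---|---|
| 5% | 4.8% | 17.1% | 17.9% | 18.2% | 13.0% |
| 10% | 4.9% | 18.1% | 19.9% | 20.5% | 13.3% |
| 20% | 5.0% | 16.7% | 19.7% | 20.8% | 12.1% |
| 30% | 4.9% | 15.6% | 19.3% | 20.5% | 11.2% |

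With 85% eligible, the shared-gate figures are 14.9% to 19.6% and the Day-14 figures 4.8% to 5.1%. Over both eligibility shares, the shared gate therefore gives 15% to 20%.

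**Pattern of concern.** When all 14 days are run, the null dose fails at Day 14 but is significant earlier in 13% to 16% of trials. This agrees with the table: at a 10% placebo rate, 20.5% − 4.9% = 15.6%.

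**Length of the sequence.** It ran at least 10 days in 64% to over 99% of trials and all 14 days in 26% to 84%.

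**Favourable direction under the stopping rule as written.** A separate simulation under the same ranges of rates and effects gives 10% to 13%. The matching nominal figure for one test is 0.05/2 = 2.5%.

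**Sensitivity to sparse early days.** Events are few on the first days, so the normal approximation is rough there. A separate run with a daily hazard of 1% to 2% and the sequence held open gave 21% over Days 14 to 1 and 17% to 18% over Days 14 to 3. The inflation does not come only from Days 1 and 2.

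**Two doses with no effect.** At least one is significant on some day in 28% to 34% of trials, against 9% to 10% with gating by dose.

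**The case against.** The strongest reply is that no promise is broken. The endpoint is exploratory, the paragraph itself disclaims adjustment, and Sections 6.6 and 6.11.2 repeat this for everything outside the graphical procedure. A rate above 5% in an analysis openly run without error control is a disclosed feature. This stands, and it limits the weight of the point. It does not settle the matter, because waiving alpha adjustment does not say which doses move on to the next day.

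A reader might infer that the SAP plans to declare an earliest day of effect for each dose. It does not say so; it speaks only of testing for differences and assessing time to response. The misreading is a risk, though a day-by-day search backward from Day 14 invites it.

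The inflation should not be overstated either. The two-sided figures include days on which the dose looks worse than placebo. All the sizes depend on assumed event rates. The case of two ineffective doses is less expected, since Section 6.1 assumes that 2 mg works on the primary endpoint.

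Finally, gating by dose has a cost. The tests are cumulative, and Section 6.2.3 itself allows for the Cox model assumptions failing. A real early effect that fades by Day 14 would be stopped at the first step. Keeping one multi-arm model running while any arm shows an effect is a defensible exploratory choice, provided that isolated early results are not read as onset.

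**Conclusion.** The point holds as a minor defect in an exploratory analysis. Read literally, the shared gate lets a dose that failed at Day 14 be tested on up to 13 more days. Its chance of at least one nominally significant day rises from about 5% to about 15% to 20%, or three to four times. In the favourable direction it is about 10% to 13%, against a nominal 2.5%.

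These figures rest on the assumed event rates, a constant daily hazard, an unadjusted log-rank test in place of the covariate-adjusted Cox model, and one effective dose that keeps the sequence open. The direction of the effect follows from the wording alone; the size does not.

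A reader might go further and infer that the trial's family-wise error is compromised. The documents do not support that: this endpoint is outside the hypotheses listed in Section 6.6, and control of the primary and key secondary endpoints is unchanged.

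**What to change.** Reword the sequence in Section 6.2.3 so that the continue-or-stop rule applies separately to each dose-versus-placebo comparison. A dose moves to the next lower day only if that dose was itself significant on the current day. Any earliest day reported for a dose is the last one in its own unbroken run starting at Day 14.

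This costs one or two sentences and needs no new data, model or alpha. It returns each ineffective dose to about 5%. It adds no adjustment across the three doses, so the chance that at least one of two ineffective doses is flagged stays at about 9% to 10%; the existing no-adjustment statement can remain.

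The downside should be stated in the SAP: a dose whose early effect fades by Day 14 is not tested earlier in this sequence. The restricted mean survival time analysis at Days 2 to 5, already planned in the same section, would still describe such an effect.
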